10.7 Participant population

As described above, all analyses will be undertaken according to the intention-to-treat principle, including all observed data on participants according to their randomised allocation. A sensitivity analysis per-protocol will exclude those who did not comply with the protocol procedures.

10.8 Procedure(s) to account for missing or spurious data

Missing and spurious data will be queried, and summarised and reported following resolution. Decisions regarding inclusion or exclusion of spurious values will be taken according to the SAP. The (mixed model) analysis will be based on all observed data on individuals and will provide robust estimation under the assumption that any missing data are missing at random (MAR), ie. where missingness can be fully accounted for by variables where there is complete information. Sensitivity analysis can test this assumption, but imputation is not planned.

10.9 Other statistical considerations

Deviations from the SAP where necessary will be reported and justified.

10.10 Economic evaluation

The economic analysis will take a health care payer perspective and seek to understand the potential impact of clinically assisted hydration as it pertains to resource utilisation. A micro

costing exercise will be undertaken to estimate the cost for each participant, for each day they are in the trial. We will also calculate the total costs, and the mean total costs, for each group separately, and then compare them. Costs will initially be expressed as a cost per participant per day because participants are likely to be in the trial for varying lengths of time. Data will be extracted from the clinical records of all participants, covering routine care and treatment of end-of-life symptoms/problems (including but not limited to treatments for delirium, audible upper respiratory secretions, pain, and shortness of breath), from the point of entry to the trial to death or withdrawal. This will include the administration of clinically assisted hydration in the relevant intervention group. The cost analysis will be comprehensive in coverage and will include monitoring the full costs of all participants in both groups, including all treatments and adverse events.

Resources utilised (medications, facilities, treatment and clinical time) will be costed using nationally validated unit costs [43], the British National Formulary [44], and NHS national costs [45], supplemented by costs from finance departments as needed. Mean daily costs will be compared between the two intervention groups, and between those experiencing delirium and those that do not. Differences in cost per day between groups will be explored using mixed effects models, recognising the cluster nature of randomisation, with intervention assignment as a covariate, adjusting for diagnosis (cancer, non-malignant disease), home country (England, Wales, Scotland, Northern Ireland), and centre as a random effect.

We are aware of the ongoing debate concerning the appropriateness of use of Quality Adjusted Life Years (QALYs) for decision-making in palliative care [46]. We decided that EQ-5D would not be suitable in this trial where participants are so close to death and may lack the ability to complete the measure. Hence, we will use a cost effectiveness measure as the primary outcome from the health economic analysis. This measure refers to the reduction in the proportion of participants developing delirium (an absolute rather than relative reduction) over the whole time the participant is in the trial from recruitment to death or 14 days. Whilst limiting the ability to use the results to inform decisions on resource allocation among palliative care interventions, the cost effectiveness outcomes might be used to benchmark other studies.

Where the statistical analysis finds a statistically significant difference between the intervention and control groups in the proportions of participants developing delirium (primary outcome), the economic evaluation will express the result as the cost per 1% reduction in the likelihood of an event. Uncertainty in input costs will be handled parametrically, sampling from

a gamma curve. Sampling uncertainty in overall differences in cost per day between groups will be handled using generalised linear mixed models.

A formal Health Economic Analysis Plan (HEAP) will be developed.

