Thus, there has been a need for further research for some time, but recent events (and the resultant change in clinical practice despite no change in research evidence) has intensified the need for a robust (adequately powered) trial of CAH at the end-of-life. Moreover, the successful completion of the CHELsea I trial [9], which achieved all of its predetermined criteria for success, supports the undertaking of such a trial (utilising a cluster randomised trial design).

The trial will also facilitate the Consortium for Hospice and Community Research (which includes the NIHR) objective to increase the number of hospices recruiting to NIHR CRN portfolio studies [22]. Thus, the trial will recruit 1600 patients from 80 sites within the UK (predominantly inpatient hospices).

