7.3 The randomisation scheme

Randomisation will be undertaken 1:1 by site (cluster), to ensure balance and equal numbers in each intervention group, stratifying by home country (i.e., England, Wales, Scotland or Northern Ireland), and by type of unit (i.e., hospital or hospice). Randomisation will be undertaken by the Trial Statistician at Surrey CTU, using a blocked randomisation with separate blocks (of random length) assigned to hospitals and hospice groups within each of the home countries to ensure balance on these factors.

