10.3.2 Primary outcome analysis

The primary analysis will use a multilevel regression approach, which recognises the hierarchical nature of the data, and participants nested within centres (clusters). A mixed effects logistic regression will be used to assess the difference in the odds of delirium (defined as a Nu-DESC score ≥ 2 at any point during the trial observation period) between intervention groups, using intervention group as a covariate and adjusting for home country (i.e., England, Wales, Scotland or Northern Ireland) and by type of unit (i.e., hospital or hospice), which were used as stratification variables in the randomisation, disease category (i.e., cancer, non-malignant disease), age (e.g., < 65 years, > 65 years), and sex (i.e., male, female). Centre will be included as a random effect, to allow for correlation in outcomes within clusters. A significance level of 5% will be used to judge significance for the primary outcome measure. The analysis will take into account different “times at risk” by adding an offset term of log (observed days to delirium) to the model, effectively adjusting the binomial denominator to reflect the number of “trials” in each participant.

A sensitivity analysis for the primary outcome will be undertaken per-protocol excluding those participants who did not comply with the protocol. Compliance with the CAH regimen will be defined as receiving $>75\%$ of the prescribed fluids.

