10.5 Adjusted analysis

Analyses will be adjusted for home country (i.e., England, Wales, Scotland or Northern Ireland) and by type of unit (i.e., hospital or hospice), which were used as stratification variables in the randomisation, disease category (i.e., cancer, non-malignant disease), age (e.g., < 65 years, $>$ 65 years), and sex (i.e., male, female) as described above.

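### The cost-per-day model in 10.10 omits type of unit, a randomisation stratifier; if daily cost differs between hospitals and hospices, the standard error of the cost difference will be too large

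*Protocol*

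**What the plan says.** Section 7.3 randomises sites 1:1, "stratifying by home country (i.e., England, Wales, Scotland or Northern Ireland), and by type of unit (i.e., hospital or hospice"), and implements this with "separate blocks (of random length) assigned to hospitals and hospice groups within each of the home countries to ensure balance on these factors".

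The primary model in 10.3.2 adjusts for home country and "by type of unit (i.e., hospital or hospice), which were used as stratification variables in the randomisation". Section 10.5 repeats both factors for the adjusted analyses.

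Section 10.10 gives the model for differences in cost per day its own list. Besides intervention assignment, the model is specified as "adjusting for diagnosis (cancer, non-malignant disease), home country (England, Wales, Scotland, Northern Ireland), and centre as a random effect". Type of unit is not in that list, and no reason is given. The same section says: "Resources utilised (medications, facilities, treatment and clinical time) will be costed using nationally validated unit costs". It assigns sampling uncertainty in the cost-per-day difference to generalised linear mixed models and promises a HEAP.

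**The concern.** The clinical models carry both stratifiers because the trial was stratified on them. The cost model keeps home country and drops type of unit.

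Cost is the outcome for which type of unit is most likely to matter, since facilities and clinical time are costed and the two settings are organised differently. Type of unit is constant within a centre. A random centre effect therefore absorbs the hospital-hospice gap as unexplained variation between centres; it does not adjust for it. Blocking has already removed most of that gap from the comparison of arms, so the model charges the contrast with variation that it largely does not have.

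Participant-level cost is a secondary endpoint in 3.2. What is at stake is an interval for the cost difference that is wider than it should be, so that a real difference may be reported as uncertain.

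**Working it through.** **Inputs from the protocol.** There are 80 centres of 20 participants (10.1), 1:1 allocation by site, and blocking within country and type of unit (7.3). The sites are described only in these words: "the trial will recruit 1600 patients from 80 sites within the UK (predominantly inpatient hospices"). The delirium ICC is 0.025 (10.1).

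**The plan's own figures.** 10.1 gives none for the cost model. Its design figures do reproduce: 60% against 50%, 90% power and two-sided 5% give 519 per arm, 1038 in all. The design effect is 1 + 19 × 0.025 = 1.475. Then 1038 × 1.475 = 1531, and 1531/0.95 = 1612, or 80.6 centres against the stated 80. So 80 × 20 is a fair basis.

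**Assumptions, because the protocol is silent.**
- Hospital share p: 12.5% to 25% of sites.
- Hospital-hospice gap d: 0, 0.25, 0.5 or 1.0 SD of participant daily cost.
- Residual cost ICC within type of unit: 0.025 (borrowed from delirium), 0.10 or 0.20.

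**Step 1: closed form under exact balance.** With equal centre sizes, the random-centre linear model is equivalent to least squares on centre means. In units of participant variance, a centre mean has variance D = ICC + (1 − ICC)/20 once type of unit is in the model. Leaving it out adds p(1 − p)d². Hence

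SE without / SE with = √(1 + p(1 − p)d² / D).

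Example: p = 0.25, d = 0.5, ICC = 0.025. D = 0.025 + 0.975/20 = 0.07375; p(1 − p)d² = 0.1875 × 0.25 = 0.0469; the ratio is √(1 + 0.636) = 1.28.

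| Gap d | ICC 0.025 (D = 0.07375) | ICC 0.10 (D = 0.145) | ICC 0.20 (D = 0.24) |
|---|---|---|---|
| 0.25 SD | 1.05-1.08 | 1.02-1.04 | 1.01-1.02 |
| 0.5 SD | 1.17-1.28 | 1.09-1.15 | 1.06-1.09 |
| 1.0 SD | 1.58-1.88 | 1.32-1.51 | 1.21-1.33 |

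Each range runs from 12.5% to 25% hospitals. At d = 0 the ratio is 1.

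**Step 2: simulation with the stratification as written.** Blocks of 2 or 4 (assumed) were used in the eight country-by-unit strata, with country in the model. The hospitals were split 7/1/1/1 (10 hospitals) or 14/2/3/1 (20 hospitals) over the four countries. The SE ratios agree with the closed form: for gaps of 0.5 and 1.0 SD they are 1.17-1.29 and 1.60-1.93 at ICC 0.025, 1.09-1.16 and 1.34-1.54 at ICC 0.10, and 1.06-1.10 and 1.22-1.36 at ICC 0.20.

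**Step 3: model SE against true sampling SD.** Small strata leave incomplete blocks, so type of unit is not perfectly balanced. At ICC 0.025, omitting it raises the true SD of the estimate by about 5-6% (gap 0.5 SD) and 15-23% (gap 1.0 SD). Part of the larger standard error is therefore real lost precision, and the rest is overstatement. Over all the ICCs and shares above, model SE divided by true SD is about 1.0-1.07, 1.04-1.27 and 1.1-1.7 for gaps of 0.25, 0.5 and 1.0 SD. With type of unit in the model, a nominal 5% test keeps a level of about 5%.

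**The case against.** **The size is not known.** This stands. The protocol gives neither the cost gap nor the hospital share, and 0.025 is a delirium ICC. More residual variation between sites in cost makes the omission matter less: at a gap of 0.25 SD and an ICC of 0.10 or more, the ratio is only 1.01-1.04. A reader might infer that the standard error is certainly too large. The documents do not support that, because with no hospital-hospice gap there is no inflation.

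**The inflation is pure over-coverage.** A reader might infer that the true sampling variation is untouched by the omission. That would need exact balance on type of unit, which random-length blocks in up to eight strata with few hospitals do not give.

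**No test is fixed for cost.** This also stands. The 5% level in 10.3.2 is set for the primary outcome, and 10.10 describes the cost differences as explored. The point therefore concerns the width of the interval. The check also assumes a normal outcome and equal centre sizes, whereas 10.10 envisages generalised linear mixed models.

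**Section 10.5 or the HEAP will cover it.** This does not answer the point. If 10.5 is read as governing every analysis, then 10.10 contradicts it. The HEAP is still to be written, but 10.10 does not leave the covariates open. A HEAP that follows its list inherits the omission.

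**Conclusion.** The omission is plain on the page and inconsistent with 7.3, 10.3.2 and 10.5. Its consequence is conditional. If daily cost differs by type of unit, which is likely given what is costed, the standard error of the cost difference is too large and some precision is lost.

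Under the stated assumptions the effect is negligible to small at a gap of 0.25 SD, modest to material at 0.5 SD, and material at 1.0 SD. The lower ends belong to high residual ICCs and few hospitals. The error is conservative. A reader might infer that it could create a false cost difference or touch the delirium result. It does neither: the cost estimate stays essentially unbiased, and the primary analysis already includes type of unit. The point is worth correcting because the remedy is nearly free.

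**What to change.** In 10.10, add type of unit (hospital, hospice) as a fixed effect to the cost-per-day mixed model, next to diagnosis, home country and the random centre effect, so that the model carries both randomisation stratifiers. Carry the same list into the HEAP, and settle it before cost data are seen so that the choice cannot appear outcome-driven.

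The cost is a one-line edit and one degree of freedom across 80 sites. No new data are needed, because 7.5 already records site of care as hospital or hospice.

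### The cost-effectiveness ratio, the main economic outcome, is to be expressed only if delirium differs significantly, and the cost model leaves out type of unit, a randomisation stratum

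*Protocol*

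**What the plan says.** Section 10.10 sets the status of the measure: "we will use a cost effectiveness measure as the primary outcome from the health economic analysis". The effect in that measure is the absolute reduction in the proportion developing delirium, from recruitment to death or 14 days. The ratio is then made conditional: "Where the statistical analysis finds a statistically significant difference between the intervention and control groups in the proportions of participants developing delirium", "the economic evaluation will express the result as the cost per 1% reduction in the likelihood of an event". Nothing is said about a non-significant result. Section 3.2 lists cost effectiveness, based on reductions in delirium, among the secondary endpoints with no such condition.

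On uncertainty, section 10.10 samples input costs from a gamma distribution and adds: "Sampling uncertainty in overall differences in cost per day between groups will be handled using generalised linear mixed models". It states no uncertainty for the ratio, or for cost and effect together.

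Total and mean total costs per group are calculated and compared, and mean daily costs are compared, whatever the delirium result. Costs are collected from entry to death or withdrawal.

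The cost-per-day model includes intervention group, "adjusting for diagnosis (cancer, non-malignant disease), home country (England, Wales, Scotland, Northern Ireland), and centre as a random effect". Section 7.3 describes randomisation as "stratifying by home country (i.e., England, Wales, Scotland or Northern Ireland), and by type of unit (i.e., hospital or hospice"). Section 10.3.2 adjusts the primary model for both strata, and section 10.5 states generally: "Analyses will be adjusted for home country (i.e., England, Wales, Scotland or Northern Ireland) and by type of unit (i.e., hospital or hospice").

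**The concern.** A cost-effectiveness result is an estimate of two quantities, incremental cost and incremental effect, with joint uncertainty. It does not follow on from a significance test. A non-significant delirium difference does not show that the effect is zero, and a decision maker still needs the estimate and its uncertainty. Making the ratio depend on the p-value does two things. It leaves a declared main outcome without a planned result in some trials. It also selects the larger observed reductions when the ratio is reported, which lowers the cost per 1% if hydration adds cost.

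The missing covariate is a smaller matter. Sites were randomised within type of unit, and the other adjusted analyses use it. Leaving it out of the cost model is inconsistent with the rest of the protocol and may widen the interval for the cost difference.

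**Working it through.** **Inputs.** Section 10.1: 60% delirium without hydration, a 10-point reduction, 90% power, 1038 evaluable, cluster size 20, intra-cluster correlation 0.025, inflation 1.475, 5% attrition, 1600 participants in 80 centres. Section 7.3: 1:1 allocation by site. Section 10.3.2: 5% significance level, taken here as two-sided. Section 10.1 ties the 60% to a score above 0, whereas the primary endpoint uses 2 or more. The 60% is taken as given.

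**The plan's own figure.** Two proportions, 0.60 against 0.50, two-sided 5%, 90% power, pooled variance, no continuity correction: 519 per arm, 1038 in total, an exact match. (The level printed in section 10.1 is 0.5, which would give 378.) Inflation is 1 + 19 × 0.025 = 1.475. Then 1038 × 1.475 = 1531, and 1531 / 0.95 = 1612, or 80.6 centres of 20, which is close to the stated 80 and 1600.

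**Standard error of the risk difference.** Effective size is 1600 × 0.95 / 1.475 = 1030.5, or 515 per arm. Using 19 evaluable per centre instead gives 1520 / 1.45 = 1048, with the same conclusions.

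- True reduction 10 points: SE = √[(0.24 + 0.25) / 515] = 0.0308.
- True reduction 5 points: SE = √[(0.24 + 0.2475) / 515] = 0.0308.

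Significance needs an observed reduction of about 1.96 × 3.08 = 6.0 points.

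**Chance of no ratio, and selection when there is one.** Two million normal draws of the risk difference were made at each true reduction. The third and fourth columns use only the draws significant in favour of hydration. The last column is the mean of 1 / observed reduction times the true reduction, that is, the mean reported cost per 1% relative to the truth for a fixed positive cost difference. Only the 10-point row is the plan's own assumption.

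| True reduction (points) | Not significant: no ratio | Mean observed reduction if significant | Mean ratio / true ratio |
|---|---|---|---|
| 10 | 10% | 10.6 | 1.00 |
| 7.5 | 32% | 9.1 | 0.87 |
| 5 | 63% | 8.1 | 0.64 |
| 3 | 84% | 7.6 | 0.40 |

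Closed-form check at 5 points: (6.03 − 5) / 3.08 = 0.33, and the upper normal tail beyond 0.33 is 0.37, so the chance of no ratio is 63%. The mean ratio is 1 − 0.64 = 36% too low.

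**Type of unit.** The protocol gives no intra-cluster correlation for cost, no hospital/hospice split and no cost difference between them, so the loss can only be illustrated. Let ρ be the cost correlation and f the share of between-centre variance explained by type of unit, with 19 evaluable per centre. The SE without adjustment, relative to the SE with it, is √{[ρ + (1 − ρ)/19] / [ρ(1 − f) + (1 − ρ)/19]}.

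- ρ = 0.025, f = 0.10: √(0.0763 / 0.0738) = 1.02.
- ρ = 0.30, f = 0.50: √(0.3368 / 0.1868) = 1.34.

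Both pairs are assumptions, and the range is too wide to serve as an estimate.

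**The case against.** The strongest reply is that only the expression as a ratio is conditional. Total and daily costs are compared regardless, the delirium difference is the primary outcome and will be reported at any p-value, and section 3.2 lists cost effectiveness unconditionally. That stands. A reader might infer that a non-significant trial would yield no economic result at all, and the protocol does not support this. What would lack a plan is the ratio, and with it any joint statement of cost and effect.

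A reader might also infer that a reported ratio will always flatter hydration. At the planned 10 points it does not: the mean observed reduction is about 6% too large, yet the mean ratio is about right. The understatement needs a smaller true effect. It also presumes that hydration adds cost, which the protocol does not state.

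A further inference is that the ratio is to be built on cost per day. Section 10.10 says costs are only initially expressed that way, and it also compares total costs. What remains is that the numerator of the ratio is not named, and that costs run to death or withdrawal while the effect runs to death or 14 days.

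On type of unit, the random centre effect absorbs hospital/hospice differences and stratification balances them across arms, so the comparison stays valid. Section 2 describes the sites as mainly hospices, so the gain from adjustment may be small. That also stands, and leaves an inconsistency and some loss of efficiency.

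Finally, a Health Economic Analysis Plan is to follow. It can properly choose the method for joint uncertainty. But the protocol already fixes the significance condition and the covariate list, and a later plan that changed them would depart from it.

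**Conclusion.** The point holds in this form and should be corrected. The protocol makes its main economic measure depend on a significance test that section 3.2 does not require. The ratio would be missing in about 10% of trials at the planned effect and about 63% at an assumed 5 points. Where reported, the mean ratio is about unbiased at 10 points and about 36% too low at 5. These figures rest on the section 10.1 inputs, a two-sided 5% test, a normal approximation and a fixed positive cost difference.

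Omitting type of unit from the cost model contradicts sections 7.3, 10.3.2 and 10.5. It loses precision by an amount that cannot be derived from the protocol. Reading it as a source of bias would be wrong.

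**What to change.** In section 10.10:

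- Delete the significance condition. Report incremental cost, incremental absolute risk of delirium and their joint uncertainty, allowing for clustering, whatever the primary p-value. Leave the method to the Health Economic Analysis Plan.
- State that the ratio uses total cost per participant, which the section already calculates, over the same window as the effect (entry to death or 14 days).
- Add type of unit to the cost model.

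This needs a change of wording, carried into the Health Economic Analysis Plan, and modest analysis work. No new data are required.

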10 STATISTICS AND DATA ANALYSIS

10.1 Sample size calculation

The sample size is based on a “clinically meaningful” reduction in the proportion of participants developing delirium in the CAH intervention group (versus the non-CAH intervention group): a figure of 10% was deemed to be appropriate by the clinicians involved in the trial, and this figure was supported by clinical colleagues (i.e., palliative care doctors / nurses), and members of the local PPI group.

To demonstrate a reduction of 10% in the proportion of participants developing delirium (defined as having a score of > 0 on the Nu-DESC scale) would require 1038 evaluable participants with 90% power and at a significance level of 0.5. The calculation assumes the incidence of delirium in the non-CAH intervention group of 60% (as observed in the feasibility trial). To account for clustering in the responses of participants within centres of size 20, the sample size will be inflated by 1.475 using an estimate of the intra-cluster correlation of 0.025 (as observed in the feasibility trial). A further allowance of 5% for attrition suggests that 80 centres will be required (delivering 1600 participants).

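### The primary health-economic result is defined only if the delirium difference is statistically significant, with nothing defined otherwise

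*Protocol*

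**What the plan says.** Protocol section 10.10 rejects QALYs for this population and states that "we will use a cost effectiveness measure as the primary outcome from the health economic analysis". The effect in that measure is the reduction in the proportion developing delirium, "an absolute rather than relative reduction", over the time in the trial up to death or 14 days.

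The next paragraph sets the condition: "Where the statistical analysis finds a statistically significant difference between the intervention and control groups" on the primary outcome, "the economic evaluation will express the result as the cost per 1% reduction in the likelihood of an event". No other expression of the result is given.

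Two other places bear on the point:

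- Section 3.2 lists cost effectiveness, tied to reductions in the likelihood of delirium, as a secondary endpoint alongside participant-level costs. It carries no significance condition.
- Earlier in 10.10, several cost analyses are planned without any condition: "We will also calculate the total costs, and the mean total costs, for each group separately, and then compare them", and "Mean daily costs will be compared between the two intervention groups, and between those experiencing delirium and those that do not".

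For uncertainty, 10.10 names gamma sampling for input costs and generalised linear mixed models for differences in cost per day. It closes with "A formal Health Economic Analysis Plan (HEAP) will be developed".

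**The concern.** Cost-effectiveness rests on the estimated incremental cost, the estimated incremental effect and their joint uncertainty. Whether the effect alone crosses p = 0.05 is not the relevant question. For the health care payer whose perspective 10.10 adopts, a non-significant reduction at little or no extra cost can still matter.

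The condition has three consequences:

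1. If the delirium test misses significance, the declared primary economic outcome, and with it part of a listed secondary endpoint, has no definition.
2. The condition refers to a difference, not a reduction. A significant increase would satisfy it, yet a cost per 1% reduction would then mean nothing.
3. When a ratio is produced, its denominator has been selected for being large. On average that overstates the reduction, and it can make the cost per point look too low.

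**Working it through.** **Inputs.** Section 10.1 gives a 60% control rate, a reduction of 10%, 90% power, 1038 evaluable participants, ICC 0.025, cluster size 20, inflation 1.475, 5% attrition, 80 centres and 1600 participants. Section 10.3.2 gives a 5% significance level; 10.1 prints 0.5, a separate slip. Section 7.3 gives 1:1 allocation by site.

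**Reproducing the plan's figure.** For 60% against 50%, two-sided 5%, 90% power, pooled variance and no continuity correction, the requirement is 519 per arm, or 1038 in total, as stated. The reduction is therefore 10 percentage points. Design effect: 1 + 19 × 0.025 = 1.475. Then 1038 × 1.475 = 1531, and 1531 / 0.95 = 1612, close to the stated 1600.

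**Standard error of the risk difference.** Evaluable: 1600 × 0.95 = 1520. Effective size per arm: 1520 / 1.475 / 2 = 515. SE = √[(0.60 × 0.40 + 0.50 × 0.50) / 515] = 0.0308, or 3.08 points. Working back from the power gives the same: 10 / (1.960 + 1.282) = 3.08.

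**Trigger.** Significance needs an observed reduction of at least 1.96 × 3.08 = 6.0 points.

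**Effect of the condition.** For a true reduction d, let a = (6.05 − d) / 3.085.

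- Chance of a significant reduction: 1 − Φ(a).
- Mean estimate given a significant reduction: d + 3.085 × φ(a) / [1 − Φ(a)].
- Mean cost per point relative to the truth, with incremental cost fixed and positive: d × E(1/estimate | significant reduction), by numerical integration.

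| True reduction (points) | a | Significant reduction | No ratio | Mean estimate if significant | Inflation of reduction | Mean cost per point / truth |
|---|---|---|---|---|---|---|
| 10 (planned) | −1.28 | 0.900 | 10% | 10.6 | 6% | 1.00 |
| 7.5 (assumed) | −0.47 | 0.681 | 32% | 9.1 | 22% | 0.87 |
| 5 (assumed) | 0.34 | 0.367 | 63% | 8.2 | 63% | 0.64 |
| 3 (assumed) | 0.99 | 0.162 | 84% | 7.7 | 156% | 0.40 |

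For example, at 5 points: 5 + 3.085 × 0.3766 / 0.3672 = 8.16, and 8.16 / 5 = 1.63.

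The last column is not the reciprocal of the inflation, because the mean of 1/x differs from 1 over the mean of x. At 10 points the average cost per point is essentially unbiased.

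**How often a significant estimate falls below the truth.** At 10 points: (0.500 − 0.100) / 0.900 = 44%.

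**Check by simulation.** Beta-binomial clusters, 40 against 40 sites, 19 evaluable each, ICC 0.025, 40,000 runs. The chance of significance and the inflation factor were 0.897 and 1.06 at 10 points, 0.364 and 1.62 at 5, and 0.162 and 2.50 at 3. Without selection, the mean estimate was 9.99 points for a true 10.

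**The case against.** The strongest reply is that the economic evaluation is much wider than this one ratio. Micro-costing, total and mean total costs by group, and mixed-model comparisons of cost per day are all unconditional, and the delirium comparison is reported whatever its p-value. A reader might infer from the condition that the trial could end with no economic answer. Section 10.10 does not support that: only the combined cost-effectiveness result may be missing.

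A reader might also infer that any ratio produced rests on an exaggerated effect, or that the cost per point is understated by as much as the effect is inflated. Neither holds. Inflation is an average; at the planned effect it is 6%, and 44% of significant estimates lie below the truth. The mean cost per point is then about right. The direction of bias at smaller effects needs an incremental cost that is positive and unrelated to the effect. The protocol gives no cost figures, and it counts delirium treatment in the costs, so the two may be correlated.

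It is also fair that joint uncertainty belongs in the HEAP. A reader might infer an interval that is too narrow, with the delirium reduction treated as known. But 10.10 specifies no interval for the ratio, so this would be inferred from silence. A significant increase in delirium is also improbable: under 0.2% at true reductions of 3 points or more.

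What does not stand is that the HEAP settles the main point. The condition is a rule stated in the protocol, not missing detail. A HEAP that follows it inherits the gap; one that drops it departs from the protocol.

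**Conclusion.** The point holds in a limited form. Section 10.10 conditions its own primary economic outcome on the significance of the delirium test, defines nothing for the other case, and conflicts with 3.2, which lists cost effectiveness unconditionally.

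At the planned 10-point reduction the consequences are modest: about one trial in ten gives no ratio, and mean cost per point is about unbiased. They grow quickly if the true effect is smaller. At 7.5, 5 and 3 points, about 32%, 63% and 84% of trials give none. If incremental cost is positive and unrelated to the effect, mean cost per point among those that do is about 13%, 36% and 60% too low.

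These figures rest on four assumptions: the 60% control rate and ICC of 0.025 from 10.1; 1520 evaluable participants; a normal approximation to the risk difference in place of the planned mixed logistic model; and true effects below 10 points, which are chosen only to show the range. The primary clinical analysis is unaffected. The change should be made because a declared endpoint is at stake and the correction is cheap.

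**What to change.** Delete the significance condition in 10.10. State that, whatever the p-value and whichever direction the difference takes, the report will give the incremental cost, the incremental absolute delirium risk, and their ratio or a statement of dominance.

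Require joint cost-effect uncertainty that respects clustering, for example by resampling whole sites within arm or by a bivariate mixed model, with details in the HEAP. Resampling within arm and every randomisation stratum should be avoided unless site counts allow it: four countries, two unit types and two arms make 16 cells for 80 sites. Some cells may hold one site or none, and a single-site cell contributes no between-site variance.

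The cost is a wording change and an analysis of data already being collected, with no effect on sample size or conduct. The downside is that the interval for the ratio may be wide or unbounded when the effect is small. Showing the incremental cost and incremental risk with their own intervals keeps the result readable in that case.
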